Sample and Justification of Sample Size: Sample size for this pilot study has been determined in discussion with [name] (collaborator, Professor & Biostatistician). Our intent is to compare arrest rates between groups and to see whether the three different regimens will yield arrest rates within a range of what we will determine to be clinically acceptable. Based on our recent pilot feasibility study of SDF with 40 children (with 239 lesions) we reported an arrest rate of approximately 96% following two applications of SDF. Results from a recent systematic review state that 80% of lesions can arrest because of SDF. We believe that a range of arrest rates from 80% to 96% yield similar beneficial outcomes in the clinical setting. Based on our pilot study, 40 children had 239 lesions (average 6 lesions/child). With our pilot sample of 239 lesions, it is possible to estimate an arrest rate with a 95% confidence interval to be accurate within $\pm 6.5\%$. With 400 lesions anticipated in our proposed recruitment sample, the 95% confidence interval for the arrest rate would be $\pm 5.0\%$. We propose three SDF regimen groups and anticipate that each group will have 22 children anticipating an average of six lesions. This would mean 396 lesions would be followed in this study. We anticipate that with 400 lesions the percent of arrest will be within $\pm 5\%$ if we have 22 children in each group. To deal with potential drop-outs and loss-to-follow-up of up to 20% we will over recruit by into each group and recruit 28 per group. We anticipate that we can successfully recruit 10 children each month.

Instrumentation and Outcome Measures: Baseline and follow-up visit questionnaires will be a modified versions of those used in our SDF pilot feasibility study (developed by [name] [collaborator] in her SDF efficacy study). The questionnaire collects child and family

demographic information, oral hygiene and use of toothpaste, dietary habits (i.e., snack foods and drinks), consumption of fluoridated water, appearance of the teeth, and symptoms (e.g., pain). The tools also include sections for the parent/caregiver to complete with their child on how the child believes their teeth look and feel and how they rated their visit and SDF treatment.

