PowerSoil Kit (Qiagen). It allows the isolation of genomic DNA (gDNA) from fungi and Gram (+-) bacteria, which will be used for downstream analyses. For the 16S rRNA (bacteriome) and ITS1 rRNA (mycobiome) amplicon sequencing, isolated gDNA will be used for PCR amplification of the V4 region of the bacterial 16S rRNA gene, and for PCR amplification of the fungal Internal Transcribe Spacer 1 (ITS1) rRNA gene. gDNA will be sequenced at Génome Québec using paired-end Illumina MiSeq PE250 sequencing. Data analysis will be performed in the [name] lab using established methods. Briefly, demultiplexed raw sequencing results will be filtered and clustered into operational taxonomic units (OTUs) and alpha and beta diversity analyses performed using QIIME2 (Quantitative Insights into Microbial Ecology) v. 2018.11. 16S sequences will be aligned and taxonomy assigned with the HOMD database. ITS1 sequences will be aligned and taxonomy assigned with the UNITE database.

Data Analysis:

This study will estimate the success of different SDF. Descriptive statistics will be used (e.g. frequencies, proportions, and means \pm standard Deviations). The “arrest rate” (primary outcome) will be calculated for the second visit and again at the third and final visit. Bivariate analyses will assess changes in clinical measures and survey data from baseline to the follow-up. McNemar’s test will be used to compare the arrest rate between the second and third clinical visits and to compare dichotomous data from the baseline questionnaire with that from the follow-up questionnaire within each regimen. Chi-squared analysis will compare arrest rates between the regimen groups. Paired t-test will be used to compare normally distributed interval data from the baseline questionnaire with that from the follow-up questionnaire within regimens (Mann-Whitney test if not normally distributed). We will rely on repeated measures analysis of variance to assess changes in ECOHIS scores and other continuous data over time (i.e. baseline vs. second visit vs. final study visit) within each regimen group and to assess differences between regimen groups. Although this is a pilot RCT, we will explore potential changes in the oral microbiome of those randomized to different regimens. This will provide insights into potential mechanisms of SDF action, whether it has antimicrobial activity and influences the oral microbiome composition. A p value ≤ 0.05 will be significant.

Ethics:

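### The ±5.0% precision behind the sample size appears to assume an unstated 50% arrest rate, independent lesions and all three regimens pooled, so it is not the precision of the regimen-specific rates to be compared

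*Combined protocol and SAP*

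**What the plan says.** All of this is in the combined protocol and SAP, under Sample and Justification of Sample Size, unless noted.

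- **Expected rates.** For the pilot, "we reported an arrest rate of approximately 96% following two applications of SDF". From the literature, "Results from a recent systematic review state that 80% of lesions can arrest because of SDF". The plan then adds: "We believe that a range of arrest rates from 80% to 96% yield similar beneficial outcomes in the clinical setting".
- **Precision.** With the pilot's 239 lesions, "it is possible to estimate an arrest rate with a 95% confidence interval to be accurate within" ±6.5%. For the new trial, "With 400 lesions anticipated in our proposed recruitment sample, the 95% confidence interval for the arrest rate would be" ±5.0%.
- **Size.** There are three regimens, and "each group will have 22 children anticipating an average of six lesions", which the plan totals to 396 lesions. Recruitment is raised to 28 per group to allow for up to 20% loss.
- **Aim.** The section says the intent is to compare arrest rates between groups and see whether they fall in an acceptable range. The Data Analysis section compares regimens by chi-squared test and calculates the arrest rate at both the second and the third visit.

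The section does not state the arrest rate used in the precision calculation, a design effect for several lesions in one child, or any power, margin or effect size. The Data Analysis section names no interval method for the arrest rate.

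**The concern.** A reader takes ±5.0% as the error bar to expect on an arrest rate from this trial. It does not correspond to either rate the plan puts forward, and it belongs to a quantity (all regimens pooled, lesions independent) that is not what the trial compares.

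Because this figure is the whole justification for 22 children per group, a reader cannot judge from it how well the trial will place each regimen relative to the 80% to 96% range. That range is 16 points wide. A per-regimen half-width of ±5% and one of ±10% or more lead to very different statements about whether a regimen lies inside it. The Significance and Future Directions section says the study will inform a larger trial, so it helps to label the figure correctly now.

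**Working it through.** **Inputs from the plan:** 95% confidence; arrest rates of 80% and 96%; 239 pilot lesions in 40 children; 400 (or 396) lesions in total; 3 groups × 22 children × 6 lesions, so 22 × 6 = 132 lesions per regimen. **Assumption not in the plan:** an ICC of lesions within a child, taken over 0 to 0.5. I follow this section in counting lesions, although the outcome section defines the arrest rate by teeth.

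**1. Reproducing the printed figures.** The half-width is z·√(p(1−p)/n). With p = 0.50 and z rounded to 2 it reduces to 1/√n:

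- n = 239: 1/√239 = 6.47%, printed as 6.5%.
- n = 400: 1/√400 = 5.00%, printed as 5.0%.

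With z = 1.96 the results are 6.34% and 4.90%. No simple binomial method (Wald, continuity-corrected, Wilson or exact) reaches the printed values at 80% or 96%. The 50% rate is therefore an inference, but a strong one. The alternative is a design effect of about 1.63 to 1.64 at 80% (ICC about 0.13 with six lesions per child), which would give the same two numbers; the plan mentions none. At 96% no ICC up to 1 would do so.

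**2. Same formula at the plan's own rates** (z = 1.96, independent lesions):

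| Lesions | 80% | 96% |
|---|---|---|
| 239 (pilot) | ±5.1% | ±2.5% |
| 400 (pooled) | ±3.9% | ±1.9% |
| 132 (one regimen) | ±6.8% | ±3.3% |

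For one regimen at 80%: 1.96 × √(0.80 × 0.20 / 132) = 6.8%. Even with no loss to follow-up, 28 × 6 = 168 lesions give 1.96 × √(0.16/168) = 6.0%. For the difference between two regimens at 80%, 6.82 × √2 = 9.65%, still with independence.

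**3. Allowing for clustering.** With six lesions per child the design effect is 1 + 5 × ICC, and the half-width is multiplied by its square root:

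| ICC | Design effect | Pooled 400, 80% | Pooled 400, 96% | Regimen 132, 80% | Regimen 132, 96% |
|---|---|---|---|---|---|
| 0 | 1.0 | 3.9% | 1.9% | 6.8% | 3.3% |
| 0.1 | 1.5 | 4.8% | 2.4% | 8.4% | 4.1% |
| 0.2 | 2.0 | 5.5% | 2.7% | 9.7% | 4.7% |
| 0.3 | 2.5 | 6.2% | 3.0% | 10.8% | 5.3% |
| 0.5 | 3.5 | 7.3% | 3.6% | 12.8% | 6.3% |

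At 80% the pooled half-width passes 5% once the ICC exceeds about 0.13. The per-regimen half-width is above 5% at every ICC.

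**4. The ceiling.** At 96%, a symmetric per-regimen interval at ICC 0.1 has upper limit 96 + 4.1 = 100.1%. From about that ICC upward, a symmetric interval for one regimen reaches or passes 100%.

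**The case against.** The strongest defence is that 50% is the usual worst-case convention. It gives an upper bound that holds at any arrest rate, and parts of the section use bound language. With independent lesions and pooling, a half-width within ±5% is true at both 80% and 96%. Nothing is miscalculated on those terms, and correcting the rate alone makes the precision look better. This stands, and it is why the assumed rate by itself is only a matter of disclosure. It does not cover the other two conditions: the bound holds neither for one regimen at 80% nor, beyond modest clustering, for the pooled rate.

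Three stronger readings are tempting, and the documents do not support them.

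- A reader might infer that the plan's 80% to 96% excludes a rate near 50%. It does not. That range describes rates of similar clinical benefit, the trial is meant to see whether regimens fall in an acceptable range, and the arrest rate is also calculated after a single application, for which no expected rate is given.
- A reader might attach the printed half-widths to 96% and object that the interval passes 100%. The plan never makes that combination, and pooled symmetric intervals at 96% with the right half-width stay below 100% (for 400 lesions, 96 ± 1.9%). The ceiling matters only per regimen with some clustering, as in step 4.
- A reader might conclude that the printed figures are 1.3 to 2.6 times too wide (5.0/3.9 and 5.0/1.9), so the trial is more precise than claimed. That holds only for pooled, independent lesions; for the comparison the trial makes at 80%, the error runs the other way.

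**Conclusion.** The point holds in a limited form. The printed ±6.5% and ±5.0% appear to be 1/√n, and ±5.0% is presented without its three conditions: a 50% arrest rate, independent lesions, and all regimens pooled. The first makes it conservative; the other two make it optimistic for the trial's own purpose.

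Per regimen at 80%, the half-width is at least ±6.8% and, for an ICC of 0.1 to 0.5, ±8.4% to ±12.8%. At 96% per regimen it runs from ±3.3% with independence to ±6.3% at ICC 0.5, so ±5% is met there only when clustering is low to moderate. Pooled at 80%, it is ±4.8% to ±7.3% over the same ICC range.

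The per-regimen result at 80% needs no assumption beyond the plan's own numbers. The clustered figures rest on the assumed ICC range and on equal numbers of lesions per child. None of this shows that the recruitment target is wrong for a pilot; it shows that the stated justification does not describe the precision of the rates to be compared.

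**What to change.** In Sample and Justification of Sample Size:

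1. State the arrest rate behind the half-width, or say that 50% is a deliberate worst case.
2. Replace the single ±5.0% with half-widths at 80% and 96%, per regimen (132 lesions) and pooled (396 lesions), over a stated ICC range. The pilot's 239 lesions in 40 children may give an ICC estimate, but at about 96% arrest only some 10 lesions (239 × 0.04) did not arrest, so a range is still needed.

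In Data Analysis:

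3. State that arrest rates will be reported with cluster-adjusted logit or Wilson-type intervals, which cannot pass 100%.

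The cost is a recomputation and a few sentences. Recruitment does not change. The drawback is that the stated per-regimen precision will look less favourable than ±5%.

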A Clinical Trial of Silver Diamine Fluoride to Arrest Early Childhood Caries in Young Children

NCT04054635

Study Protocol and Statistical Analysis Plan

15 April 2019

Purpose:

To investigate the effectiveness of using silver diamine fluoride (SDF) to arrest early childhood caries in very young children randomized to different application frequency regimens. We will also study potential oral microbiome changes in children receiving SDF treatment.

Hypotheses:

1. Two applications of SDF at different frequencies will yield similar arrest rates.
2. SDF will negatively influence the population of cariogenic bacteria in the oral microbiome.

Objectives (*primary objective, †secondary objectives):

1. Determine the effectiveness of various application regimens of SDF to arrest caries*;
2. Determine potential changes to the oral microbiome in young children†; and
3. Determine the impact on early childhood oral health related quality of life†.

Methods:

Design: We propose a RCT to study the use of SDF to arrest cavitated caries lesions in primary teeth at different application regimens. Regimen 1 will be two applications of SDF four months apart, which is the protocol frequency adopted by the Winnipeg Regional Health Authority's Clinical Guideline on SDF. This frequency was used in a pilot study. Regimen 2 will be two applications of SDF six months apart (American Dental Association's [ADA] recommendation). Regimen 3 will be two applications of SDF one month apart, which is proposed in the American Academy of Pediatric Dentistry's clinical practice guideline. The ADA recently indicated that SDF should be prioritized over 5% NaFV for nonrestorative management of cavitated lesions. Thus, we will not include a control group to receive fluoride varnish as this would now be considered unethical and substandard care. However, we will attempt to follow as a comparison group those children whose parents/caregivers do not consent to SDF to manage their child's caries and only choose 5% NaFV.

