The Early Childhood Oral Health Impact Scale (ECOHIS) will be used to assess changes in OHRQL from baseline to completion of study. ECOHIS is a validated tool for use with parents/caregivers of children < 72 months of age. It consists of 13 questions grouped into two sections: 1) child impact, and 2) family impact. The child impact section includes nine questions in four areas: 1) symptoms, 2) functions, 3) psychology, and 4) self-image and social interaction. The family impact component covers two areas: 1) parental distress and 2) family function. Each question is scored from 0 to 5 [0= never, 1= hardly ever, 2= occasionally, 3 = often, 4= very often, 5= don't know]. A total score for each child is calculated by summing up response codes. The ECOHIS will allow us to calculate and compare mean ECOHIS scores at each visit and between groups. Our team has experience with analyzing ECOHIS.

Clinical outcomes assessed will include the proportion of teeth arrested (i.e., "arrest rate" = total number teeth arrested / total number of teeth treated), the proportion of children with any arrested caries, associated morbidity (dental pain and, dental abscess assessed using the PUFA index), and proportion of children requiring dental surgery under GA. The PUFA index is a score of the consequences of severely decayed teeth with visible pulpal involvement (P/p), ulceration caused by dislocated tooth fragments (U/u), fistula (F/f) and abscess (A/a). We will also record dmft and dmfs scores for each child at baseline and at subsequent study visits. The dmft and dmfs scores are cumulative counts of the total number of primary teeth or surfaces decayed, missing due to, or filled because of caries.

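### ECOHIS scoring gives *don't know* code 5, above *very often* at 4, and sums the codes, so as written every *don't know* inflates the secondary quality-of-life total

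*Combined protocol and SAP*

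**What the plan says.** Instrumentation and Outcome Measures describes the instrument: "It consists of 13 questions grouped into two sections: 1) child impact, and 2) family impact". On scoring it says "Each question is scored from 0 to 5", with the codes "0= never, 1= hardly ever, 2= occasionally, 3 = often, 4= very often, 5= don't know". The scoring rule follows: "A total score for each child is calculated by summing up response codes". The same paragraph says the instrument will be used to "calculate and compare mean ECOHIS scores at each visit and between groups".

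Data Analysis takes the scores into "repeated measures analysis of variance to assess changes in ECOHIS scores and other continuous data over time", within each regimen and between regimens. The measure serves a secondary objective in the Objectives list: "Determine the impact on early childhood oral health related quality of life".

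No section sets code 5 to missing, excludes it, prorates or imputes it, or limits how many such answers a usable total may contain.

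**The concern.** Codes 0 to 4 are ordered frequencies, and a higher code means a more frequent problem. *Don't know* is not a point on that scale. Giving it 5 and summing the codes treats a non-answer as the worst possible answer, so the total no longer ranks children by impact.

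The mean total is the quantity to be compared, so the error passes directly into the reported quality-of-life result. Three consequences need to be kept apart:

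- **Level.** Mean scores are too high at every visit where anyone answers *don't know*.
- **Change over time.** If the *don't know* rate falls between visits, part of the recorded improvement is an artefact; if it rises, there is false worsening. If the rate is constant and unrelated to the true answer, no change is invented, but a true change is shrunk.
- **Regimen comparison.** A false difference arises if *don't know* rates differ by regimen after randomisation. Under the same assumption, equal rates shrink a true difference.

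**Working it through.** The plan states no ECOHIS total or range, so there is no figure of its own to reproduce. The check applies its scoring rule directly.

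**Inputs from the documents (Instrumentation and Outcome Measures).** There are 13 items, of which 9 are child impact ("The child impact section includes nine questions in four areas"), leaving 13 − 9 = 4 family impact. Substantive codes run 0 to 4, and *don't know* = 5.

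**Inputs assumed, because the documents give none.** *Don't know* rate per item q = 2%, 5% or 10%; mean true item code m = 0.5 to 2; *don't know* unrelated to the true answer unless stated otherwise.

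**1. Range of the total**

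| | Codes 0–4 only | As written |
|---|---|---|
| Child impact | 9 × 4 = 36 | 9 × 5 = 45 |
| Family impact | 4 × 4 = 16 | 4 × 5 = 20 |
| Total | 13 × 4 = 52 | 13 × 5 = 65 |

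**2. One answer.** Replacing a true code t by 5 adds 5 − t: 5 points if the truth is never, 1 if it is very often. It is never zero or negative. For a child whose other 12 items average 1, one *don't know* gives 12 × 1 + 5 = 17, against 13 × 1 = 13 if that item also averaged 1, an excess of 4.

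**3. Mean inflation.** The expected item code is (1 − q)m + 5q, which exceeds m by q(5 − m). Over 13 items the excess is 13 × q × (5 − m).

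| q | m = 2 | m = 0.5 |
|---|---|---|
| 2% | 13 × 0.02 × 3 = 0.78 | 13 × 0.02 × 4.5 = 1.17 |
| 5% | 13 × 0.05 × 3 = 1.95 | 13 × 0.05 × 4.5 = 2.93 |
| 10% | 13 × 0.10 × 3 = 3.90 | 13 × 0.10 × 4.5 = 5.85 |

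**4. Rate changes between visits, true score unchanged.** A fall from 10% to 2% gives false improvement of 13 × 0.08 × 3 = 3.12 (m = 2) to 13 × 0.08 × 4.5 = 4.68 (m = 0.5). A rise of the same size gives equal false worsening.

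**5. Rate differs between regimens.** With m = 1, a difference of 2, 5 or 10 percentage points gives a false mean difference of 13 × 0.02 × 4 = 1.04, 13 × 0.05 × 4 = 2.6 or 13 × 0.10 × 4 = 5.2.

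**6. Constant rate.** The 5q term cancels, so recorded change = (1 − q) × true change. If the item mean falls from 1.0 to 0.5, the true change is 13 × (−0.5) = −6.5. It is recorded as 0.95 × (−6.5) = −6.18 at 5%, or 0.90 × (−6.5) = −5.85 at 10%.

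**7. *Don't know* related to the true answer.** Let t₁ and t₂ be the mean true codes behind the *don't know* answers at two visits. At a constant rate, recorded change = true change − 13 × q × (t₂ − t₁). Since t₂ − t₁ lies between −4 and 4, the distortion can reach 13 × 0.05 × 4 = 2.6 points at 5%, or 13 × 0.10 × 4 = 5.2 at 10%, in either direction. These are outer limits, not expected values. They show that the cancellation in step 6 depends on the assumption.

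**The case against.** The strongest reply concerns weight, not fact. ECOHIS serves a secondary objective, neither stated hypothesis concerns quality of life, the sample size does not use it, and the plan calls the trial a pilot. The sizes above rest on assumed rates, and the documents give neither a standard deviation nor an important difference for ECOHIS against which to judge a shift of 1 to 5 points. The fall from 10% to 2% means about one fewer *don't know* per child (13 × 0.08 = 1.04), and nothing in the documents points to such a fall. At a constant rate, the loss on a true change of −6.5 is only 0.3 to 0.65 points. The plan also describes ECOHIS as validated and the team as experienced with it, so 0 to 5 may be a loose account of form codes that would be cleaned before scoring.

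Most of this stands as a limit on size. The practical effect is unknown and could be small if *don't know* is rare and stable. It does not cure the text: experience is not a scoring rule, and an analyst following the plan would sum the 5s. Differing rates are possible, though not shown: visits are 1, 4 or 6 months apart by regimen, some families will need interpreters, and the second-visit description does not say, as the baseline and final ones do, that an interviewer administers the questionnaire.

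**Conclusion.** The concern holds. The scoring rule is wrong as written, not merely short of detail: it ranks a non-answer above the worst substantive answer and extends the total from 52 to 65. That each *don't know* raises the total by 1 to 5 points follows from the codes alone.

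The effect on means depends on a rate the documents do not give. Under the stated assumptions it is about 0.8 to 1.2 points at 2%, 2.0 to 2.9 at 5% and 3.9 to 5.9 at 10%. False change or false regimen differences need differing rates or, at equal rates, a link between *don't know* and the true answer that itself differs between visits or regimens. The primary outcome is untouched. This should be fixed before analysis, but it does not threaten the trial's main result.

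**What to change.** In Instrumentation and Outcome Measures, state that items are scored 0 to 4 only and that *don't know* is set to missing before summing, neither added as a code nor counted as zero.

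Pre-specify a missing-item rule. One option is to replace a missing item with the mean of the child's answered items in the same section when at least half are answered (at least 5 of 9 child items, at least 2 of 4 family items), and otherwise to set that section and the total to missing. Report *don't know* counts by visit and regimen, so that readers can see whether non-answers differ.

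The cost is one or two sentences and a recode in the database. No new data are needed provided the item responses, and not only totals, are stored in REDCap; that should be confirmed. The downside is that a few totals may be missing. Settling the rule before analysis also avoids a scoring choice made after the results are seen.

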Third visit: Depending on the regimen children will return 4 months (Regimen 1), 6 months (Regimen 2), or 1 month (Regimen 3) later for their final follow-up visit. Parents/caregivers will complete a follow-up questionnaire administered by interviewer. Caries lesions that were treated with applications of SDF will be assessed to see if caries is arrested. Caries lesions will be assessed for colour change, size, and clinical hardness. We will also record dmft, dmfs, and PUFA scores. Clinical data will be recorded on the Clinical Record Form.

Clinical data from baseline and each follow-up visit will be linked with questionnaire data. Data will be entered into a REDCap database and saved on the secure server at CHRIM.

Oral Microbiome Sub-Study: SDF may inactivate cariogenic bacteria in vitro. There was only one study that conducted RNA analysis of plaque in six children before and after treatment (3 receiving SDF and 3 placebo) reporting no changes in relative abundance of cariogenic bacteria. In that study, not only was sample size a major limitation, but the lead author is a director of Advantage Arrest™. Our proposal to assess 30 children would provide statistical power and help elucidate if SDF leads to changes in the oral bacteriome and mycobiome. This will provide novel insights into SDF's mechanism of action, whether antimicrobial, remineralization, or both. Ten children from each regimen will have plaque samples collected. Samples will be obtained at baseline (prior to SDF application), at the first follow-up visit (prior to SDF application), and at the final visit. Nucleic acid isolation from plaque samples will be done using the DNeasy

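### The primary arrest rate is defined per tooth, but the planned precision and the 80% benchmark are stated per lesion, and nothing in the plan links the two units

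*Combined protocol and SAP*

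**What the plan says.** **Outcome.** Instrumentation and Outcome Measures gives the only operational definition of the arrest rate: "total number teeth arrested / total number of teeth treated". Data Analysis names the arrest rate as the primary outcome, to be calculated at the second and third visits, and restates no unit.

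**Sizing.** Sample and Justification of Sample Size works in lesions.
- On the pilot: "40 children had 239 lesions (average 6 lesions/child".
- On the trial: "This would mean 396 lesions would be followed in this study".
- On precision: "With 400 lesions anticipated in our proposed recruitment sample, the 95% confidence interval for the arrest rate would be" ±5.0%.

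**Benchmark.** The lower end of the 80% to 96% range is explicitly per lesion: "Results from a recent systematic review state that 80% of lesions can arrest because of SDF". The upper end comes from the pilot: "we reported an arrest rate of approximately 96% following two applications of SDF". That sentence also gives the number of pilot lesions but does not state the denominator of the 96%.

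**Assessment of arrest.** Hardness, colour and size are recorded for lesions at every visit. For the final visit, Implementation says: "Caries lesions that were treated with applications of SDF will be assessed to see if caries is arrested".

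**The concern.** A tooth can carry more than one cavitated lesion. The plan itself keeps the two apart: the baseline examination records teeth, tooth surfaces and tooth numbers, and separately the location of each eligible lesion. A rate per tooth and a rate per lesion are therefore different quantities unless every treated tooth has exactly one lesion.

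Two items are needed to move between them: the number of lesions per tooth, and a rule for when a tooth with several lesions counts as arrested. The documents give neither. The same section does set an any-lesion rule for the proportion of children with arrested caries, but nothing comparable for teeth.

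Two readings are at stake: the planned precision, and whether each regimen falls inside the range that the plan calls clinically acceptable. If the unit and the rule stay open, they could also be chosen after the results are seen.

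**Working it through.** **Inputs from the plan:** 239 pilot lesions, 400 and 396 planned lesions, 22 children per group in three groups, six lesions per child, a 95% interval, benchmarks of 80% and 96%.
**Assumed, because the plan gives no figure:** lesions per tooth L from 1 to 2, and the within-tooth correlation ρ of arrest.

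**1. Reproduce the plan's figures.** Planned total: 22 × 3 × 6 = 396 lesions. Half-width = 1.96 × √(p(1−p)/n), at p = 0.5:
- n = 400: 1.96 × √(0.25/400) = 4.90 points. With the continuity correction 1/(2n) it is 5.03. Stated: 5.0.
- n = 239: 1.96 × √(0.25/239) = 6.34 points. With the correction it is 6.55. Stated: 6.5.

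At n = 400, p = 0.80 gives 3.92 and p = 0.96 gives 1.92. The stated figures therefore correspond to p = 0.5, with all lesions pooled over the three groups and treated as independent.

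**2. Same formula with teeth as the unit**, n = 396/L:

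| L (assumed) | Teeth | p = 0.5 | p = 0.80 | p = 0.96 |
|---|---|---|---|---|
| 1.0 | 396 | ±4.9 | ±3.9 | ±1.9 |
| 1.25 | 317 | ±5.5 | ±4.4 | ±2.2 |
| 1.5 | 264 | ±6.0 | ±4.8 | ±2.4 |
| 2.0 | 198 | ±7.0 | ±5.6 | ±2.7 |

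**3. How far ±5 points holds.** Teeth needed = p(1−p) × (1.96/0.05)².
- p = 0.5: 384 teeth, so L up to 396/384 = 1.03.
- p = 0.80: 246 teeth, so L up to 396/246 = 1.61.

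**4. What 80% of lesions means in teeth.** Assume half the treated teeth have one lesion and half have two (L = 1.5), with the same arrest probability p for every lesion. For a two-lesion tooth, P(both arrest) = p² + ρp(1−p), and P(at least one) = 2p − P(both). The tooth rate is 0.5p plus half of P(both) under an all-lesions rule, or 0.5p plus half of P(at least one) under an any-lesion rule. With p = 0.80:

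| ρ (assumed) | P(both) | All lesions arrest | Any lesion arrests | Spread |
|---|---|---|---|---|
| 0 | 0.64 | 72% | 88% | 16 points |
| 0.5 | 0.72 | 76% | 84% | 8 points |
| 1 | 0.80 | 80% | 80% | 0 |

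At p = 0.96 and ρ = 0, P(both) = 0.9216, so the tooth rates are 94% (all) and 98% (any).

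**The case against.** The best case for leaving the text alone is that the mismatch may do no harm. With one lesion per treated tooth, the rate, the benchmark and the interval are all unchanged. At the lowest rate the plan calls acceptable, 80%, ±5 points holds up to about 1.6 lesions per tooth. Independence within a tooth is a wide case, and correlation narrows the gap between the two rules. All three regimens would use the same unit, so the mismatch does not in itself bias the comparison between them. A tooth-level outcome is also workable: eligibility is set by tooth, and dmft and the baseline tooth counts are recorded.

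All of this stands, and it limits what can be claimed. A reader might infer that the trial has fewer units than planned, that ±5% is lost, or that the 80% to 96% range is simply wrong for this outcome. The documents do not support that, because each inference needs a number of lesions per tooth that they do not give. Nor are all assessments per lesion; only the grading that bears on arrest is. The lesion basis of the 96% is the natural reading, not a stated fact.

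What the objection does not supply is the missing rule or the missing number. Without them a reader cannot tell whether the harmless case applies.

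**Conclusion.** The conflict is in the text and is not just missing detail: the primary outcome is per tooth, while its precision statement, its lower benchmark and the grading of arrest are per lesion. The planned ±5% and the 80% to 96% range cannot be carried over to the outcome as defined.

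The size is conditional. It is nil at one lesion per tooth. At 1.5 lesions per tooth the half-width is ±6.0 points at p = 0.5 but ±4.8 at p = 0.80. A regimen with a lesion rate exactly at the 80% floor could sit up to 8 points below or above it on the tooth scale in the illustrated case, depending on the unstated rule, with less movement as within-tooth correlation rises.

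The point should be settled before analysis. It concerns the benchmark reading and the precision statement; it does not show bias between regimens. Two other limits on the same ±5%, pooling of the groups and independence of lesions within a child, are separate matters and are not resolved by fixing the unit.

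**What to change.** In Instrumentation and Outcome Measures, define the primary arrest rate as lesions arrested divided by lesions treated. State in Data Analysis that the lesion is the unit for the arrest-rate analyses. This matches the sample size section and the way arrest is graded. A per-tooth rate can be kept as a secondary outcome with its rule written down: a tooth is arrested when all its treated lesions are arrested.

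If teeth are kept as the primary unit, state that rule and restate both the precision and the acceptable range in teeth. This needs a figure for lesions per tooth. The plan says it reuses the pilot's record forms, so the pilot data may supply one. In either case, state the denominator of the 96% pilot rate.

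The lesion option costs one definition and one sentence on the unit, since lesion data are already collected and no visit or measurement is added. Two changes should not be brought in with it. Allowing for clustering of lesions within child alters the tests named in Data Analysis and needs its own decision. Restricting the denominator to lesions that were re-examined would change how losses are handled, which this inconsistency does not justify.
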